Protocol Component	Description under target trial	Description under Emulation
Eligibility Criteria	Adult inpatients receiving B-lactam therapy for culture confirmed monomicrobial invasive GAS between who can be randomized within 72h of index culture	Adult inpatients receiving B-lactam therapy for culture confirmed monomicrobial invasive GAS between the years 2015-2021 in the PINC AI™ dataset who receive anti-toxin within 3 days of index culture.
Treatment strategies	B-lactam therapy as primary therapy for GAS started within (+/-) 3 days of index GAS culture and continued for a minimum of 3 consecutive days. Adjunctive anti-toxin (clindamycin vs. linezolid) therapy started within (+) 3 days of culture.	Same as target trial.
Assignment procedures	
Patients will be randomly assigned within 3 days of culture (grace period) to clindamycin vs. linezolid. Investigators and patients and will be aware of the strategy to which they have been assigned (pragmatic, unblinded, open-label non-inferiority).
 
Switching between linezolid and clindamycin will not be permitted under the protocol.
	
Patients will be assigned to the anti-toxin therapy compatible with their observed treatment. Difference in baseline characteristics and confounding by indication will be addressed through the creation of a propensity weighted cohort.
 
Those who received both agents within the eligibility period will be excluded.

Follow up period	Starts at time of randomization (anti-toxin initiation) and ends at death, discharge to hospice, loss to follow up or 90 days, whichever occurs earliest.	Starts at time of anti-toxin initiation and ends at death, discharge to hospice or discharge from the hospital to home or facility or administrative censorship on Jan 31 st 2022.
Outcome	
Primary outcome: Time to all-cause mortality (or discharge to hospice) censored at 90 days.
 
Secondary outcome: infection attributable 90-day mortality, all-cause in-hospital mortality, 90-day disease reoccurrence, length of stay following anti-toxin administration among survivors, occurrence of CDI
	
Primary outcome: All-cause in-hospital mortality (or discharge to hospice)/ time to death (days).
 
Secondary outcome: Length of stay following anti-toxin administration among survivors, occurrence of CDI requiring treatment following anti-toxin administration.

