requiring treatment following anti-toxin administration up to 90 days, occurrence of serotonin surge syndrome while on therapy.

Causal contrast of interest	Intention-to-treat effect; per-protocol effect.	Observational analog to Intention-to-treat effect and per-protocol effect.
Analysis plan	Intention-to-treat and per protocol effects estimated via comparison of adjusted 90 day in-hospital mortality risk assigned to each treatment strategy.	
Intention-to-treat and per protocol effects estimated via comparison of adjusted in-hospital mortality risk assigned to each treatment strategy.
 
To account for confounding by indication a propensity score (PS) will be generated based on the probability of receiving linezolid using the patient and center level variables selected a priori based on clinical judgment, . Overlap weighting on a propensity-score between the two groups will be performed with downstream adjustment for ICU stay , shock and debridement/source control.

Abbreviations: CDI: Clostridioides difficile infection; GAS: Group A streptococcus.

The study was designed in accordance with the trial emulation approach described by Hernán and Robins¹⁹. The study aims to emulate a hypothetical target pragmatic multi-center, non-blinded trial.

Eligibility

Adult inpatients patients (≥ 18 y of age) with culture confirmed proven or probable (see below) invasive monomicrobial GAS in the PINC AI™ database between 2015-2021 who receive a β -lactam for a minimum of 3 days within 3 days of culture will be eligible for inclusion in the emulated trial. Patient will be included if they then receive anti-toxin therapy within 3 days of culture being drawn, as long as B-lactam therapy has been initiated prior or on the same day as antitoxin therapy.

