Statistical analysis will be performed with R using Rstudio V2022.12.0.353 (R Foundation for Statistical Computing, Vienna, Austria). The reporting of the study will be in line with Strengthening the Reporting of Observational Studies in Epidemiology (STROBE) reporting guidelines²⁰

Sensitivity analysis

The following sensitivity analysis will be performed:

- Analysis of patients with proven GAS only (excluding those with probable GAS)
- Analysis where hospital as a random effect is not included
- An analysis which includes those who receive anti-toxin +/-3 days of index therapy to capture those treated empirically prior to culture results.
- An analysis without PS weighting and only downstream logistical regression (as would be done in a classical observational study).
- An analysis utilizing cloning methodology to account for potential immortal time bias²¹

Subgroup Analysis

We will use similar methods as for the primary analysis to assess the impact of allocation to either treatment group on the following prespecified subgroups

- Patients with NSTI or TSST
- Patients with pressor dependent shock
- Patients admitted to the ICU within one day (+/-) of index GA eligibility culture
- Excluding patients with who received clindamycin that had a clindamycin non-susceptible isolates (defined as resistant or intermediate or a positive D-test)
- Excluding patients with who received clindamycin that had a clindamycin non-susceptible isolates or had clindamycin antimicrobial susceptibility testing missing
- Stratified by days of anti-toxin therapy (>1, >2, >3 days)

Missing Data Plan

Less than 5% missingness across key variables is expected

References

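### The cloning sensitivity analysis states no cohort or time zero, and in the plan's own cohort of anti-toxin recipients it would not be informative about immortal time bias

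*Combined protocol and SAP*

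**What the plan says.** The cloning item is the last of five bullets under Sensitivity analysis: "An analysis utilizing cloning methodology to account for potential immortal time bias". It cites a methods paper and adds nothing further.

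The cohort is defined elsewhere:
- **Receipt of an anti-toxin.** Table 1 limits the emulation to patients "who receive anti-toxin within 3 days of index culture". The Eligibility section repeats the condition: "Patient will be included if they then receive anti-toxin therapy within 3 days of culture being drawn".
- **One agent only.** Table 1 and Exclusion Criteria remove patients who received both agents.
- **Beta-lactam completion.** Exclusion Criteria remove patients with fewer than 3 days of beta-lactam.
- **Assignment.** "Patients will be assigned to the anti-toxin therapy compatible with their observed treatment".
- **Follow-up in the emulation.** "Starts at time of anti-toxin initiation".

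The target trial column of Table 1 is wider. It needs only patients "who can be randomized within 72h of index culture", and it states a grace period: "Patients will be randomly assigned within 3 days of culture (grace period) to clindamycin vs. linezolid".

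**The concern.** Cloning handles a grace period by starting the clock before the treatment is known. A copy of each patient enters every strategy, and a copy is censored when it departs from its strategy. Deaths before either drug is started then count in both copies. This needs patients who were eligible but not yet treated, including those who died or left hospital untreated. The plan's cohort has none of them.

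This is the only listed analysis aimed at immortal time bias. The study tests noninferiority with a 5-point margin, so an uninformative check matters most if the bias lowers apparent mortality on linezolid. That happens if linezolid tends to be started later in the 3-day window, because its recipients have then survived longer after culture before being classified.

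**Working it through.** The plan gives no figure on this point, so there is none to reproduce. Steps 1 and 2 rest on the documents alone. Step 3 uses assumed rates.

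**1. Which cohort the item uses.** Two other sensitivity bullets change the population and say so: proven infection only, and the anti-toxin window widened to either side. The cloning bullet states no change, so the natural reading is the main cohort.

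**2. Two possible time zeros in that cohort.**
- *Anti-toxin initiation.* Each patient's agent is known at time zero. The opposite clone is censored at once, and what remains is the primary comparison, apart from the choice of weights.
- *Index culture.* Inclusion requires having lived to receive the drug, so deaths between culture and initiation are zero by construction for up to 3 days. No weighting of survivors restores the excluded deaths.

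**3. Illustration under a true null.** Assumptions:
- The daily death probability is h on days 0 to 2 after culture and 0.15% afterwards. It is the same on either drug or untreated. The horizon is 30 days and there is no confounding.
- Daily start probabilities on days 0 to 3, clindamycin then linezolid:
  - equal timing: 0.30, 0.15, 0.08, 0.04 and 0.075, 0.0375, 0.02, 0.01
  - linezolid later: 0.35, 0.15, 0.06, 0.03 and 0.03, 0.05, 0.06, 0.05
  - much later: 0.40, 0.12, 0.04, 0.02 and 0.01, 0.03, 0.07, 0.08

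*Primary analysis.* For a patient starting on day k, 30-day risk from initiation = 1 − (1 − h)^(3−k) × (1 − 0.0015)^(27+k). With h = 2% this is 9.619%, 7.913%, 6.175% and 4.403% for k = 0, 1, 2, 3. Start-day shares among initiators in the later scenario are 0.726, 0.189, 0.059, 0.026 (clindamycin) and 0.274, 0.277, 0.261, 0.188 (linezolid).
- Clindamycin: 0.726 × 9.619 + 0.189 × 7.913 + 0.059 × 6.175 + 0.026 × 4.403 = 8.96%
- Linezolid: 0.274 × 9.619 + 0.277 × 7.913 + 0.261 × 6.175 + 0.188 × 4.403 = 7.27%
- Difference: 7.27 − 8.96 = −1.69 points, when the truth is 0.

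*Cloning from culture.* On each of days 0 to 2, clones that did not start the other agent are weighted by 1/(1 − q), where q is that day's probability of starting the other agent. Clones still untreated at day 3 are weighted up to represent starting their own agent. In the initiator-only cohort, untreated days carry no deaths.

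Linezolid minus clindamycin, percentage points, h = 2%:

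| Start timing | Primary | Cloning, initiators only | Cloning, all beta-lactam patients |
|---|---|---|---|
| Equal | 0.00 | −1.90 | 0.00 |
| Linezolid later | −1.69 | −2.28 | 0.00 |
| Linezolid much later | −2.93 | −2.96 | 0.00 |

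Over h = 0.5% to 4%, initiator-only cloning ranges from −0.49 to −3.70 (equal), −0.58 to −4.45 (later) and −0.75 to −5.79 (much later). Cloning in all beta-lactam patients stays at 0.00. With equal timing the spurious difference arises because linezolid is the rarer agent: its clones spend longer in the untreated days, which are death-free by selection.

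The table leaves out the 3-day beta-lactam rule. At h = 2%, applying it shrinks the initiator-only result to about −0.5 to −1.2, because the rule already removes many early deaths from both arms. Cloning in all beta-lactam patients stays at about 0.

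**The case against.** **The plan is silent on the cohort.** The bullet cites a methods paper, and the sponsor may intend a wider cohort. This stands. It cannot be shown that the analysis will be run among initiators only; that is the natural reading of a list whose other population changes are stated. The edit needed is the same either way.

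**The culture-to-initiation gap is not follow-up time.** In the emulation, follow-up "Starts at time of anti-toxin initiation and ends at death" or another end point, and the target trial also starts its clock at randomisation, which it equates with initiation. Patients who die earlier belong to neither arm of the primary comparison. This stands too. In the primary analysis the gap acts as survivor selection before follow-up, and it differs by arm only if start times differ. Immortal time inside follow-up comes instead from the 3-day beta-lactam completion rule and the both-agents exclusion, which can depend on events after time zero. Cloning in the same cohort undoes neither.

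**A reader might infer that the check would falsely reassure.** The documents do not support that. Close agreement with a biased primary result appears only in some timing scenarios (−2.93 against −2.96). With equal timing the check departs from an unbiased primary result (−1.90 against 0.00), which would alarm rather than reassure.

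**A reader might also put a firm size on the bias.** For example, 1% mortality per day times a 1-day later start gives 1 point, or 1/5 of the margin. Both inputs are assumed, and the sum ignores the 3-day beta-lactam rule.

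**It is one of five sensitivity analyses.** True, and the primary analysis is not affected by this point. But no other listed analysis addresses this bias.

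**Conclusion.** The concern holds in a limited form. As written, and on the natural reading, the cloning analysis inherits a cohort selected on having received exactly one anti-toxin within 3 days of culture and on completing 3 days of beta-lactam. In that cohort it either repeats the primary comparison or runs through a grace period with no pre-initiation deaths. It can agree with a biased primary result or differ from an unbiased one, so neither outcome tells the reader whether the bias is present.

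This rests on the cohort definition and needs no assumed rate. The size does need assumed rates: the documents give no distribution of start days and no early death rates, so the modelled differences carry over only qualitatively. It is a point the sponsor should correct before the analysis is run, in one sensitivity analysis.

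**What to change.** Rewrite the cloning bullet, for this sensitivity analysis only, to state:
- **Time zero:** index culture, or the first beta-lactam day if later.
- **Cohort:** all otherwise eligible patients who started a beta-lactam, regardless of later anti-toxin receipt, receipt of both agents, or completion of 3 beta-lactam days.
- **Strategies:** each patient cloned into starting clindamycin by day +3 and starting linezolid by day +3.
- **Events:** deaths and hospice discharges before censoring counted in both clones.
- **Censoring:** at deviation from the assigned strategy, that is, on receiving the other agent before its own, or at the end of day +3 if nothing was started. Say also whether a later switch counts as deviation, since Table 1 lists both intention-to-treat and per-protocol analogues.
- **Estimation:** inverse-probability-of-censoring weights, with bootstrap intervals.

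Reporting the distribution of anti-toxin start day by arm would also show whether the survivor selection described above can differ between arms.

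The cost is a wider pull from the same database, plus programming. Because many patients may never start an anti-toxin, the weights will be more variable and the interval wider, especially for linezolid.

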 - Description: *C. difficile* positive (PCR or antigen) result within same encounter downstream of the antitoxin therapy within 30 days and/or presence of a non present on admission (POA) *C. difficile* diagnosis code in conjunction with receipt of *C. difficile* therapy (PO/rectal vancomycin or PO fidaxomicin or IV metronidazole)

Statistical Analysis Plan

To account for confounding by indication a propensity score (PS) will be generated based on the probability of receiving linezolid using the patient and center level variables. Variables thought to be associated with a clinician's decision to initiate adjunctive treatment with linezolid (vs. clindamycin) and with mortality will be selected for inclusion. Overlap weighting on a propensity-score between the two groups will be performed with downstream adjustment for ICU stay, shock and debridement/source control. To take the clustered data structure into account, matching on center will be attempted if feasible, if not, propensity scores will be calculated using a mixed effects model with hospital as a random effect. Covariate balance between the two groups before and after generation of the weighted cohorts will be assessed by examining the standard mean difference for variables across the exposure categories.

Power calculation

Because no randomized clinical trials have previously compared adjunctive treatment options for GAS, the sample size estimation was derived from the largest retrospective study available³. In that study the overall in hospital mortality in adjunctive clindamycin group 6.5% in the propensity matched cohort. A published abstract, the only other published clinical data on the topic, found mortality between linezolid (n=26) and clindamycin (n=26) groups to be similar (clindamycin 11.5% and linezolid 7.7%)²¹. This was confirmed by preliminary exploration of GAS blood stream infection cases in our dataset (clindamycin 10%, linezolid 12%).

Based on a mortality rate of 6.5% in the both groups as the most conservative estimate and a noninferiority margin of 5% with 1:4 allocation ratio, 1035 patients (828 clinda + 207 Linezolid) will be needed in total to achieve 80% power with a 2-sided α level of 0.05, allowing for 10% dropout. A 5% noninferiority margin was chosen as the maximal difference in mortality between treatments that would be clinically acceptable, by consultation with infectious disease, critical care specialists within the study team.

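### Subgroups are analysed one at a time with no treatment-by-subgroup contrast, so the plan cannot show whether the linezolid–clindamycin effect differs in the sickest patients

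*Combined protocol and SAP*

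**What the plan says.** The Subgroup Analysis section of the combined protocol and SAP states its method in one sentence: "We will use similar methods as for the primary analysis to assess the impact of allocation to either treatment group on the following prespecified subgroups". Six bullets follow:

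- three severity subgroups: NSTI or toxic shock, pressor-dependent shock, and ICU admission within a day either side of the culture;
- two restrictions that remove clindamycin-treated patients according to susceptibility results;
- one stratification by duration of anti-toxin therapy with three cut-offs.

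Counting the cut-offs separately gives eight analyses.

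The primary method is in the Statistical Analysis Plan section: "Overlap weighting on a propensity-score between the two groups will be performed with downstream adjustment for ICU stay, shock and debridement/source control". That paragraph contains no margin and no decision rule. The margin appears only under Power calculation: "A 5% noninferiority margin was chosen as the maximal difference in mortality between treatments that would be clinically acceptable". Noninferiority as a design appears only in the target-trial column of Table 1: "pragmatic, unblinded, open-label non-inferiority".

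For the subgroups, the document states no between-subgroup contrast, ordering, error control, exploratory label, expected size or power.

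**The concern.** Asking whether the effect differs by severity means comparing the effect in a subgroup with the effect in its complement. Separate analyses inside each subgroup do not make that comparison. Adjusting for shock and ICU stay in the primary model does not make it either, because a main effect of shock is not an interaction of shock with treatment.

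The severity rows are the ones clinicians will read most closely. The background section says adjunctive clindamycin is recommended for severe invasive disease and associated NSTI, and that clinical experience with linezolid is limited. With no stated rule for reading a subgroup result, the 5-point margin is the benchmark a reader is likely to reach for. A small, high-mortality subgroup can miss that margin because of its size and event rate alone, and the miss could then be taken as evidence that linezolid does worse in the sickest patients.

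**Working it through.** **Inputs from Power calculation.** "Based on a mortality rate of 6.5% in the both groups as the most conservative estimate"; "a noninferiority margin of 5% with 1:4 allocation ratio"; "80% power with a 2-sided α level of 0.05, allowing for 10% dropout"; "1035 patients (828 clinda + 207 Linezolid) will be needed in total". Subgroup shares and subgroup mortality are not in the document and are assumed below. The only nearby figure is the preliminary bloodstream-infection mortality of 10% (clindamycin) and 12% (linezolid).

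**Step 1: reproduce the plan's figure.** With p = 0.065 in both arms, margin 0.05 and n_C = 4·n_L, the unpooled formula is n_C = 5·p(1−p)·(z_α + z_β)²/0.05².

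- One-sided 0.05: 5 × 0.060775 × (1.645 + 0.842)²/0.0025 gives 752 + 188 = 940. Multiplying by 1.1 gives 828 + 207 = 1035, an exact match.
- One-sided 0.025: 955 + 239 = 1194. Multiplying by 1.1 gives 1314, which does not match.

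The stated total therefore corresponds to one-sided 0.05, although a two-sided level of 0.05 would usually be read as one-sided 0.025. Both levels are carried below.

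**Step 2: chance of meeting the margin inside a subgroup when the agents are equal.** P = Φ(0.05/SE − z), with SE = √[p(1−p)(1/n_L + 1/n_C)], taking the subgroup as a share of 207 + 828.

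Example with a 20% share (41 + 166) and 12% mortality: SE = √[0.1056 × (1/41.4 + 1/165.6)] = 0.0565, so P = Φ(0.885 − 1.96) = 0.14.

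| Share | Mortality | One-sided 0.025 | One-sided 0.05 |
|---|---|---|---|
| 20% | 12% | 0.14 | 0.22 |
| 20% | 20% | 0.11 | 0.18 |
| 30% | 12% | 0.19 | 0.29 |
| 30% | 20% | 0.14 | 0.22 |
| 50% | 12% | 0.29 | 0.40 |

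**Step 3: met overall but missed in the subgroup.** This was a nested binomial simulation with equal agents, 207 + 828 patients and overall mortality fixed at 6.5%. Among simulated studies that met the margin overall, the severe subgroup missed it as follows.

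- 20–30% share, 12–20% mortality: 67–80% at one-sided 0.025 and 61–74% at one-sided 0.05.
- 50% share, 12% mortality: 54% and 47%.

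These are conditional figures. At one-sided 0.025 the margin is met overall in only 73–74% of studies. The joint pattern (met overall, missed in the subgroup) therefore occurs in 49–59% of studies for 20–30% shares, and in 39% for a 50% share at 12% mortality.

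**Step 4: family error, a separate hypothesis.** This supposes that each of the eight analyses is read as a two-sided 0.05 difference test and the agents are equal. Independence would give 1 − 0.95⁸ = 33.7%, but the duration strata are nested and the other analyses overlap. Simulating the overlap (5,000 runs per scenario, unweighted comparisons) gave:

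- 16.7% with severity shares of 50/40/60% and 95/85/70% of patients retained at the three cut-offs;
- 23.3% with severity shares of 20/10/30% and 80/50/30% retained.

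Other scenarios fell between these. The range is about 17–23%, or 3.3–4.7 times 0.05.

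**Step 5: precision of the contrast.** The detectable interaction at 80% power is (1.96 + 0.842)·√(V_sub + V_comp), where each V is p(1−p)(1/n_L + 1/n_C), on a base of 188 + 752.

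| Share | Mortality, subgroup / complement | Detectable difference in risk differences |
|---|---|---|
| 40% | 15% / 4% | 14.1 points |
| 30% | 20% / 5% | 17.7 points |
| 20% | 30% / 5% | 24.1 points |

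**The case against.** The strongest reply is that the plan claims little for its subgroups. It makes no confirmatory statement about them, and it never says that the margin or any alpha is applied inside one. The method it carries over is weighting and adjustment, not a verdict. On that view the gap is one of labelling, and a contrast with 14–24 points detectable would add little.

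Much of this stands, and it rules out four stronger readings that a reader might infer.

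- *That the plan tests noninferiority in each subgroup.* The document does not say so. Steps 2 and 3 describe what would follow if someone did.
- *That noninferiority overall with failure in the sickest is the expected output for equal agents.* The joint pattern is only 49–59% for 20–30% shares and 39% in the 50% case. All of these rest on assumed shares and mortality. Some combinations are strained: a 30% subgroup at 20% mortality leaves (6.5 − 0.3 × 20)/0.7 = 0.7% in everyone else. In addition, 1035 is the number required, not the cohort available.
- *That the false-positive rate is about seven times alpha.* That figure needs independence, which nested and overlapping analyses cannot have. It also concerns difference tests. If the agents are equal, a finding of noninferiority is correct, so the margin result and the family error should not be run together.
- *That formal alpha control is required.* With no confirmatory subgroup claim, it is not.

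The reply does not answer the main point. A label alone would not let the stated method address whether the effect varies by severity. Imprecise contrasts are a reason to show that uncertainty and to withhold subgroup verdicts.

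**Conclusion.** The point holds in a limited form. The method stated for the subgroups cannot show whether the effect differs by severity, and that follows from the text without any assumption. The numerical consequences are conditional. If the margin were used inside subgroups, a miss after overall success would be the more likely result for equal agents when the subgroup is 20–30% of the cohort, and roughly an even chance at half the cohort with 12% mortality. If the subgroups were read as difference tests, the family error would be about 3–5 times the nominal level. All figures use unweighted binomial variances, so they do not include the effect of overlap weighting on precision. The primary analysis is unaffected; the exposure is in how the subgroup results are read. The change is a worthwhile and inexpensive improvement.

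**What to change.** Replace the opening sentence of Subgroup Analysis with wording to this effect:

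> For NSTI or toxic shock, pressor-dependent shock and early ICU admission, the subgroup analysis is the difference between the overlap-weighted risk differences in the subgroup and in its complement, with a 95% CI. Risk differences and CIs within subgroups are descriptive. The 5-point margin is not applied within subgroups, and neither noninferiority nor failure to show it is concluded there. All subgroup analyses are exploratory and not adjusted for multiplicity.

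Give the susceptibility and duration bullets the exploratory label only. No clean interaction contrast exists for them: the first two drop patients from one arm, and the duration strata are nested and defined after treatment starts.

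The cost is a change of wording and three contrasts from data already in hand. The intervals will be wide, as Step 5 shows, and the sponsor gives up standalone noninferiority statements in subgroups.

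### Membership of the ICU and shock subgroups can be decided after anti-toxin treatment has begun, so these subgroup contrasts can be biased

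*Combined protocol and SAP*

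**What the plan says.** All references are to the combined protocol and SAP.

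- **Time zero.** Table 1, follow-up row, emulation column: "Starts at time of anti-toxin initiation and ends at death, discharge to hospice or discharge from the hospital to home or facility".
- **When time zero can fall.** Table 1, treatment strategies: "Adjunctive anti-toxin (clindamycin vs. linezolid) therapy started within (+) 3 days of culture". The Eligibility section agrees: "Patient will be included if they then receive anti-toxin therapy within 3 days of culture being drawn".
- **ICU subgroup.** Subgroup Analysis: "Patients admitted to the ICU within one day (+/-) of index GA eligibility culture".
- **Shock subgroup.** Subgroup Analysis: "Patients with pressor dependent shock". No timing is given.
- **Purpose and method.** The subgroup section opens: "We will use similar methods as for the primary analysis to assess the impact of allocation to either treatment group". The primary method is overlap weighting on a propensity score, with later adjustment for ICU stay, shock and source control.

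Nowhere does the plan require ICU admission or shock to be present by the first anti-toxin dose.

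**The concern.** A subgroup meant to show the effect of allocation should be fixed by what is known at time zero. Here the ICU rule is tied to a different date, the culture, and the shock rule to no date. Some patients can therefore enter a subgroup because of how they fared after starting one agent or the other.

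Suppose one agent prevents more early deterioration. Its subgroup then holds fewer late entrants, and the two arms of the subgroup differ in make-up even if they matched at time zero. Overlap weights built to balance characteristics at treatment choice do not undo selection on a later event. The cloning sensitivity analysis is aimed at immortal time and does not redefine subgroup membership.

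These are the severely ill patients, for whom readers will most want the comparison. The Background section gives some reason to expect a difference between agents, since it cites rising clindamycin resistance. The exclusion criteria remove linezolid-resistant isolates from the linezolid arm, with no matching exclusion for clindamycin outside two separate subgroup analyses.

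**Working it through.** The plan states no figure on this point, so there is none to reproduce. The check has two parts.

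**1. The ICU window against each permitted start day** (days counted from culture; the window covers −1, 0 and +1)

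| Anti-toxin start | Window days before start | Same day, order unknown | Window days after start |
|---|---|---|---|
| 0 | −1 | 0 | +1 |
| +1 | −1, 0 | +1 | none |
| +2 | −1, 0, +1 | none | none |
| +3 | −1, 0, +1 | none | none |

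Entry that is clearly after treatment is possible only for day 0 starts. Day +1 starts are exposed only through same-day order. For day +2 and +3 starts the window closes before treatment. Their later pre-treatment ICU admissions (for example day +2 before a day +3 start) are left out, but that exclusion cannot depend on the agent. The shock subgroup has no window, so no start day is protected by the text.

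**2. How large the shift could be, with no effect of either agent on death**

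All rates here are assumptions. Let b be the share of an arm in the ICU at time zero, with mortality m_b. Let d be the share admitted after starting, with mortality m_d. Subgroup mortality in an arm is

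R = (b·m_b + d·m_d) / (b + d).

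Take b = 30% or 40% in both arms, and d = 5% in one arm against 10% or 15% in the other. Differences are the arm with fewer transfers minus the arm with more.

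*Late entrants die less often (m_b 18–20%, m_d 5–8%)*
- Smallest: (0.40×0.18 + 0.05×0.08)/0.45 = 16.9%; (0.40×0.18 + 0.10×0.08)/0.50 = 16.0%. Difference +0.9 points.
- Largest: (0.30×0.20 + 0.05×0.05)/0.35 = 17.9%; (0.30×0.20 + 0.15×0.05)/0.45 = 15.0%. Difference +2.9 points.

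*Late entrants die more often (m_b 12%, m_d 20%)*
- Smallest: (0.40×0.12 + 0.05×0.20)/0.45 = 12.9%; (0.40×0.12 + 0.10×0.20)/0.50 = 13.6%. Difference −0.7 points.
- Largest: (0.30×0.12 + 0.05×0.20)/0.35 = 13.1%; (0.30×0.12 + 0.15×0.20)/0.45 = 14.7%. Difference −1.5 points.

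*No shift.* If m_b = m_d, then R = m_b in both arms. If d is equal in both arms, R is equal too.

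*Only some patients start on day 0.* The figures above apply d to the whole arm. If d is instead the rate among day 0 starters and a share s of the arm starts on day 0, replace d by s·d:
- s = 50%: +0.9 to +2.9 becomes +0.5 to +1.8. Upper end: (0.060 + 0.00125)/0.325 = 18.85% against (0.060 + 0.00375)/0.375 = 17.00%.
- s = 25%: it becomes +0.3 to +1.1. Upper end: (0.060 + 0.000625)/0.3125 = 19.40% against (0.060 + 0.001875)/0.3375 = 18.33%.

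*A second set of assumptions.* Let 20% be in the ICU before treatment with 20% mortality. Of day 0 starters on clindamycin, 10% enter on day +1 with 12% mortality, and 25–75% of patients start on day 0. Linezolid changes late entry by a ratio of 0.5 to 2. The extremes of linezolid minus clindamycin come at 75%:
- Ratio 0.5: 18.74% − 17.82% = +0.92 points.
- Ratio 2: 16.57% − 17.82% = −1.25 points.

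**The case against.** The other side has a good case, and much of it stands.

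- **A reader might infer that the contrasts are distorted.** The documents do not show this. In the model above, bias needs the agents to differ in later ICU entry and late entrants to differ in mortality from those already in the ICU. No figure in the plan speaks to either.
- **A reader might infer bias in both directions of misclassification.** Leaving out an ICU admission on day +2 before a day +3 start makes the subgroup narrower. It is settled before treatment, so it does not make the arms differ.
- **A reader might infer that the plan counts pressors begun at any later time.** The text is silent on timing. What can be said is that it does not exclude late shock. The illustration models the ICU subgroup only, so the shock point carries no figure.
- **The upper end is generous.** It applies late-entry rates to whole arms. Its inputs also sit badly with the planned overall mortality of 6.5%: in the largest case, ICU deaths alone in the higher-transfer arm are 0.30×0.20 + 0.15×0.05 = 6.75% of that arm. They fit better with the 10% and 12% preliminary bloodstream figures in the Power calculation section.
- **The 5% non-inferiority margin is no yardstick here.** It was set for the sample-size comparison, and no subgroup non-inferiority test is stated.
- **Imprecision is larger.** Take the largest case with the planned arms, linezolid having fewer transfers: 207×0.35 = 72 and 828×0.45 = 373 patients. An unweighted 95% interval has half-width 1.96×√(0.179×0.821/72 + 0.150×0.850/373), about 9.5 points.

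The mismatch of dates itself remains. It is in the text, nothing else in the plan removes it, and a wide interval does not excuse a bias that can be avoided.

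**Conclusion.** The point holds in a limited form. For day 0 starts, and possibly day +1 starts, membership of the ICU subgroup can be decided after treatment begins. The shock subgroup has no stated timing and so does not rule this out for any start day. If the agents differ in early deterioration, the contrasts can be biased towards either agent.

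The size is not computable from the documents. Under the assumed rates it is about 0 to 3 points, at most about 1.8 if half of patients start on day 0 and about 1.1 if a quarter do. Only subgroup results are at stake, and this rule does not touch the primary result. Whether ICU stay and shock are suitably timed as adjustment variables in the primary model is a separate question, though the same date rule would serve there.

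**What to change.** In the Subgroup Analysis section, define both subgroups by status at time zero:

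- The patient is in the ICU, or has pressor-dependent shock, on or before the calendar day of the first anti-toxin dose, whatever the start day.
- Either keep a stated lower limit (such as the existing day −1 from culture) or require the status to be ongoing at time zero. Without one of these, an ICU stay that ended before treatment would count.
- ICU admission or pressor start after that day does not count.
- State how same-day events are handled.

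The cost is a changed date condition on data already in use and a line or two in the SAP. Subgroup sizes will change slightly: late entrants leave, and some late starters already in the ICU join. With day-level data, same-day order stays uncertain under any rule.
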